7.6 Follow-up of subjects withdrawn from treatment

These subjects will be followed-up by usual care protocols.

7.7 Premature termination of the study

Since the study is comparing two ways of usual care, there are no reasons for premature termination of the study.

8. SAFETY REPORTING

8.1 Temporary halt for reasons of subject safety

In accordance to section 10, subsection 4, of the WMO, the sponsor will suspend the study if there is sufficient ground that continuation of the study will jeopardise subject health or safety. The sponsor will notify the accredited METC without undue delay of a temporary halt including the reason for such an action. The study will be suspended pending a further positive decision by the accredited METC. The investigator will take care that all subjects are kept informed.

8.2 AEs, SAEs and SUSARs

8.2.1 Adverse events (AEs)

Adverse events are defined as any undesirable experience occurring to a subject during the study, whether or not considered related to the trial procedure. All adverse events reported spontaneously by the subject or observed by the investigator or his staff will be recorded.

8.2.2 Serious adverse events (SAEs)

A serious adverse event is any untoward medical occurrence or effect that

- results in death;
- is life threatening (at the time of the event);

-
- requires hospitalisation or prolongation of existing inpatients' hospitalisation;
 - results in persistent or significant disability or incapacity;
 - is a congenital anomaly or birth defect; or
 - any other important medical event that did not result in any of the outcomes listed above due to medical or surgical intervention but could have been based upon appropriate judgement by the investigator.

The investigator will report all SAEs to the sponsor without undue delay after obtaining knowledge of the events, except for the following SAEs:

- side-effects of antibiotics treatment
- elective hospital admission for nonsurgical treatment

The sponsor will report the SAEs through the web portal *ToetsingOnline* to the accredited METC that approved the protocol, within 7 days of first knowledge for SAEs that result in death or are life threatening followed by a period of maximum of 8 days to complete the initial preliminary report. All other SAEs will be reported within a period of maximum 15 days after the sponsor has first knowledge of the serious adverse events.

SAEs not requiring reporting like mentioned above will be listed annually in a report.

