7.3 Study procedures

Nonsurgical treatment

Patients in the nonsurgical treatment group will be treated following a nonsurgical treatment policy. This policy consists of relative rest (stop exercise, bed rest), wound care with sterile bandages and pressure bandage; hospital admission may be considered. On day 16 wound classification, clinical examination and CRP are performed. In case of persistent leakage at day 16, a DAIR according to study protocol is advised on days 17-20.

Surgical treatment

DAIR on day 10. DAIR is meant to clean the prosthesis and the wound in order to conquer the possibility of infection. DAIR consists of opening the wound, taking one culture from the fluid deep in the fascia and at least four deep-tissue cultures: two synovial and at least one around both components of the joint prosthesis. Only after taking cultures are antibiotics started and the hematoma and necrosis excised. Mobile parts (e.g. tibial insert, femoral

head) are exchanged to make room for optimal debridement. The wound is lavaged thoroughly with 3-6 litres of saline. Scrub sponges are used to mechanically clean all visible prosthetic parts. Povidone iodine solution or chlorhexidine solution may be used as additional intraoperative antiseptic.

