8.4 Follow-up of adverse events

All AEs will be followed until they have abated, or until a stable situation has been reached. Depending on the event, follow up may require additional tests or medical procedures as indicated, and/or referral to the general physician or a medical specialist.

SAEs need to be reported till end of study within the Netherlands, as defined in the protocol.

8.5 [Data Safety Monitoring Board (DSMB) / Safety Committee]

Since the study is comparing two ways of usual care a DSMB is not necessary.

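### Section 8.2.2 exempts antibiotic side-effects from prompt SAE reporting without a severity limit, and exempts planned admission for nonsurgical treatment while saying nothing about planned admission for DAIR

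*Protocol*

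**What the plan says.** Protocol section 8.2.2 opens its definition with "A serious adverse event is any untoward medical occurrence or effect that" meets one of several criteria. Death and threat to life are among them, and so is an occurrence that "requires hospitalisation or prolongation of existing inpatients' hospitalisation". Investigators send all SAEs promptly to the sponsor "after obtaining knowledge of the events, except for the following SAEs", and two kinds follow: "side-effects of antibiotics treatment" and "elective hospital admission for nonsurgical treatment". The sponsor then notifies the ethics committee (METC) "within 7 days of first knowledge for SAEs that result in death or are life threatening"; other SAEs have 15 days. Exempt SAEs go into a yearly list.

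On treatment, section 7.3 makes antibiotics a step of DAIR: "Only after taking cultures are antibiotics started and the hematoma and necrosis excised". Section 4 says the same. The nonsurgical policy in sections 4 and 7.3 names no antibiotics, makes admission optional, and advises a DAIR on days 17-20 if the wound still leaks at day 16. Section 10.2 allows the allocated DAIR on day 10 or 11.

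On oversight, section 8.5 states: "Since the study is comparing two ways of usual care a DSMB is not necessary". Section 9.4 (interim analysis) and section 8.3 (annual safety report) are both marked not applicable.

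**The concern.** There are two separate problems.

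**The antibiotic exemption is open-ended.** It is defined by cause, with no limit on outcome, so it overrides the section's own faster route for deaths and life-threatening events. Section 8.1 obliges the sponsor to suspend the study when safety is in doubt. That duty depends on the sponsor knowing of the event. With no DSMB and no interim look, the protocol gives no second prompt route.

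**The admission exemption names one treatment only.** By listing a planned admission among the excepted SAEs, the section itself treats such an admission as an SAE. It does not say whether planned admission for DAIR is to be treated in the same way. Sites must decide for themselves, and the decision arises mainly in the surgical arm.

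At stake are the speed with which the gravest drug reactions become known and whether the promptly reported SAEs mean the same thing in both arms.

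**Working it through.** The protocol states no figure on this point, so the check sets its rules side by side.

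**Step 1. Route of a fatal or life-threatening event (section 8.2.2)**

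| Cause | Investigator to sponsor | Sponsor to METC |
|---|---|---|
| Any cause outside the two exemptions | Prompt | 7 days from the sponsor's first knowledge |
| Antibiotic side-effect | Exempt | Clock may not start; annual list only |

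The METC clock is tied to the sponsor's knowledge, so exempting the investigator's report removes the usual trigger. An event just after one yearly list could wait until the next: up to about 365 days against 7, a difference of up to 365 - 7 = 358 days. Because section 8.3 is marked not applicable, the list would presumably travel with the progress report in section 11.4, which does cover SAEs.

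**Step 2. Status of planned admissions (section 8.2.2 against sections 4, 7.3 and 10.2)**

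| Planned admission or prolonged stay | Exempt? |
|---|---|
| Elective, for nonsurgical treatment | Yes, and called an SAE |
| For allocated DAIR, day 10-11 | Not mentioned |
| For DAIR on days 17-20 in the nonsurgical arm | Not mentioned; DAIR is not nonsurgical treatment |

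Two readings of the unmentioned rows are possible:

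- *Reading A.* Planned admission for bed rest is classed as an SAE, so planned admission for DAIR is one too. It is not exempt and must be reported.
- *Reading B.* A scheduled procedure is not an untoward occurrence, so it is not an SAE. On that logic elective admission for bed rest would not be one either, and its exemption would be unnecessary.

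The text does not choose between them.

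**Step 3. Which arm each exemption touches**

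The admission exemption can apply only to nonsurgical treatment. On the wording of sections 4 and 7.3, the antibiotic exemption bears mainly on the surgical arm, plus nonsurgical patients who go on to a late DAIR. However, the Summary's rationale lists antibiotics under nonsurgical usual care, while the Summary's intervention paragraph and sections 4 and 7.3 do not. Those places must be reconciled before the balance between arms can be stated firmly.

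**Step 4. Scale of extra reporting (assumption only)**

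The protocol gives no rate of serious antibiotic reactions. If 1% to 3% of the 194 patients planned for the surgical arm (section 3.4) had one, that would be 194 × 0.01 = 1.9 to 194 × 0.03 = 5.8, or about 2 to 6. Fatal or life-threatening reactions would be a subset of these.

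**The case against.** The strongest reply is that the exemptions govern speed of reporting and not collection. Section 8.2.1 records every adverse event that is reported or observed, and exempt SAEs are listed yearly. This stands: harm data are retained, and a complete comparison between arms can still be made at the end. How SAEs are tabulated is normally left to the analysis plan, which is not shown, and is not criticised here.

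A reader might infer that every patient allocated to DAIR generates a reportable SAE while nonsurgical admissions never do. The documents do not support that. The definition requires an untoward occurrence, and the protocol never says that a planned DAIR admission is one. The nonsurgical exemption may also be meant only to clarify an optional admission. Further, it covers elective admission for nonsurgical treatment alone; admission in that arm for a complication is not exempt.

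A reader might also infer that SAEs are the only measure of harm. They are not: all adverse events are recorded, second surgery is a study parameter (section 7.1.2), and the primary endpoint, revision for PJI, is itself a harm outcome. Nor is it settled that only DAIR brings antibiotics, given the Summary's rationale and the late DAIR option.

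None of this answers the missing severity limit or the silence on planned DAIR admission.

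**Conclusion.** The point holds as a defect in the prompt-reporting rules. As written, an antibiotic reaction that kills or threatens life may miss both the sponsor and the 7-day METC route and surface only in a yearly list. Separately, the status of planned DAIR admission is undefined while its nonsurgical counterpart is expressly exempt, so promptly reported SAE counts may differ between arms and sites because of the rules and not the treatments.

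The size is a matter of timing: up to about a year instead of 7 days. How many events are affected cannot be calculated, since the protocol gives neither a reaction rate nor the share of patients still leaking at day 16. The conclusion assumes that sites follow section 8.2.2 literally and that the sponsor does not learn of the event by another route. It does not extend to lost harm data or to an invalid final safety comparison.

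**What to change.** Amend section 8.2.2 in two places:

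- **Antibiotics.** Limit the exemption to side-effects that are neither fatal nor life-threatening, so that those two categories follow the prompt route whatever their cause.
- **Planned admission.** Apply one rule to both arms: exempt from prompt reporting the planned admission or prolonged stay for allocated or protocol treatment, including the protocol DAIR on day 10-11 and on days 17-20. State that complications of such an admission remain reportable.

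Separately, reconcile the Summary's rationale with the Summary's intervention paragraph and sections 4 and 7.3 on whether antibiotics belong to nonsurgical treatment, so that it is clear to whom the first exemption applies.

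The cost is a short amendment and a few additional prompt reports. Sites that now report planned DAIR admissions would send fewer. No new data are needed, because section 8.2.1 already records all adverse events, and patient care is unchanged.

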8.2.3 Suspected unexpected serious adverse reactions (SUSARs)

NA

8.3 Annual safety report

NA

8.4 Follow-up of adverse events

All AEs will be followed until they have abated, or until a stable situation has been reached. Depending on the event, follow up may require additional tests or medical procedures as indicated, and/or referral to the general physician or a medical specialist.

SAEs need to be reported till end of study within the Netherlands, as defined in the protocol.

8.5 [Data Safety Monitoring Board (DSMB) / Safety Committee]

Since the study is comparing two ways of usual care a DSMB is not necessary.

9. STATISTICAL ANALYSIS

Statistical analyses will be performed with the help of IBM SPSS statistics 22. An intention to treat analyses will be performed. For all analyses a one-tailed significant level of $p < 0.05$ is considered to be statistically significant

9.1 Primary study parameter(s)

Clinical outcome

This study is designed as a randomized controlled trial. Every patient can be classified as nonsurgical or surgical. At least two measurements will be collected, namely before the

intervention (at day 9) and one year after the intervention. Between these two measurements additional information on the patient will be collected. The patient is also nested within a hospital, but the dependency of the measurements within the patient is our focal interest. The primary outcome of the study is revision surgery for PJI within one year (a binary variable). To take into account all these dependencies, multilevel logistic regression model with three levels will be used to analyse the data. The three levels are hospitals, patients and measurements, where measurements are nested within patients and patients are nested within hospitals. The effect of the intervention will be controlled with covariates such as age and gender.

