7.1.2 Secondary study parameters/endpoints (if applicable)

Study parameters are wound class, temperature, CRP, culture results, second surgery. Patient parameters include BMI, ASA, smoking, medication.

Disease specific and general health related quality of life. The short HOOS and KOOS and the Oxford Hip and Knee Score will be used as disease-specific outcome instruments. The EQ-5D-5L will be used as a generic health-related quality of life questionnaire. To get an impression of pain an NRS will be used. All questionnaires are recommended by the Netherlands Orthopaedic Association (NOV) and are included in the standard Patient Reported Outcome Measure (PROM) for both TKA and THA patients. In Dutch hospitals it is standard procedure that patients fill in these questionnaires preoperatively and at 3, 6 and 12 months postoperatively.

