9.2 Secondary study parameter(s)

Secondary outcomes are disease-specific and general health-related quality of life (ordinal variables). In line with the analyses of the primary outcome, a multilevel linear regression model with three levels will be used to analyse the data. The three levels are hospitals, patients and measurements, where measurements are nested within patients and patients are nested within hospitals. The effect of the intervention will be controlled with covariates such as age and gender.

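### Section 9.1 fits a three-level repeated-measurement logistic model to an outcome that occurs once per patient, so the size of the treatment odds ratio depends on row coding and variance handling

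*Protocol*

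**What the plan says.** Protocol section 9.1 defines the endpoint as follows: "The primary outcome of the study is revision surgery for PJI within one year (a binary variable"). It also says "At least two measurements will be collected", and the two occasions it names are before the "intervention (at day 9) and one year after the intervention". Other patient information is gathered in between, but the section does not say that revision status is recorded repeatedly or how several rows per patient would be coded.

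It then states that "the dependency of the measurements within the patient is our focal interest" and that a "multilevel logistic regression model with three levels will be used to analyse the data". The levels are spelled out: "The three levels are hospitals, patients and measurements, where measurements are nested within patients and patients are nested within hospitals". Age and gender are given as examples of covariates.

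Section 9.2 carries the same structure over to quality of life: "a multilevel linear regression model with three levels will be used to analyse the data". Those scores are repeated. Section 7.1.2 says that "patients fill in these questionnaires preoperatively and at 3, 6 and 12 months postoperatively".

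**The concern.** A measurement level with a patient random effect needs at least two informative responses per patient. The primary outcome gives one. Section 3.2 admits patients whose wound is still leaking at day 9 after a primary arthroplasty, and day 9 comes before the intervention. Revision status at that visit is therefore zero for everyone by design.

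The structure suits the quality-of-life scores in section 9.2 but not a single yes or no. This is the confirmatory clinical analysis. If it is run as written, the analyst must decide what the extra rows are, whether to include a time term and what to do with the patient variance. The protocol settles none of these, and each can move the reported odds ratio although the patients' outcomes are the same.

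**Working it through.** **1. Inputs.** Section 3.4: 20% revised for PJI under nonsurgical treatment, a 50% reduction with DAIR, 80% power, level 0.05, 155 per group, 194 after 20% dropout. Section 9: one-tailed level of 0.05.

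**2. The plan's own figure.** Two proportions, one outcome per patient, unpooled variance, one-sided:

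n = (1.645 + 0.842)² × (0.20 × 0.80 + 0.10 × 0.90) / 0.10² = 6.18 × 0.25 / 0.01 ≈ 155.

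Dropout: 155 / 0.80 = 193.75, so 194. Both figures are reproduced. The trial was sized on one binary value per patient.

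**3. Test data.** 31/155 (20.0%) versus 16/155 (10.3%), the nearest whole numbers to plan. The plain odds ratio, surgical versus nonsurgical, is (16/139) / (31/124) = 0.46.

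**4. One informative row per patient.** With a patient random intercept of standard deviation σ, the risk in group g is the average of expit(α + βg + σu) over a standard normal u. The likelihood depends on the data only through these two averaged risks. For any σ, α and β can be chosen to return exactly 20.0% and 10.3%, so the data cannot choose σ.

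| Patient SD | Log-likelihood | Odds ratio exp(β) |
|---|---|---|
| 0 | -129.04 | 0.46 |
| 1 | -129.04 | 0.42 |
| 2 | -129.04 | 0.32 |
| 3 | -129.04 | 0.23 |
| 5 | -129.04 | 0.11 |

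The likelihood-ratio statistic for treatment is 5.73 at every SD.

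**5. Day-9 rows plus a time term.** All day-9 values are zero, so the time term separates them perfectly. They add nothing to the likelihood, and the problem reduces to step 4.

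**6. Day-9 rows without a time term.** The likelihood has a definite maximum at SD 0 (-163.78, against -166.04 at SD 1). The structural zeros count as non-events, so the modelled risks become 31/310 = 10% and 16/310 = 5%. The odds ratio is (16/294) / (31/279) = 0.49 and the likelihood-ratio statistic is 5.26.

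**7. Cumulative status at 3, 6 and 12 months as rows.** This layout is an assumption. The times are borrowed from the questionnaire schedule, and the event timing (50%, 25%, 25% by interval) is assumed too.
- Without time terms, the likelihood peaks near SD 7.5 with an odds ratio of about 0.05.
- With time terms, it was still rising at every SD tried up to 15. The odds ratio was 0.07 at SD 6 and 0.007 at SD 12.

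Once revised, a patient stays revised. The within-patient correlation is therefore built in by the coding.

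**Limits of the check.** Steps 4 to 7 leave out the hospital level and covariates, and were not run in the software that section 9 names.

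**The case against.** The strongest reply is that little harm reaches the inference. In the flat case the treatment test is the same at every SD and the fitted marginal risks stay at the observed 20% and 10%. Software that sets the patient variance to zero returns the ordinary odds ratio. The day-9 coding without a time term is misspecified rather than unidentified, and its 0.49 lies close to 0.46. All of this stands.

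A reader might infer more: that the model must fail to converge, that the treatment comparison is meaningless, or that it cannot recover the 20% versus 10% contrast. The documents do not support these readings. Convergence in the planned software was not tested, and in the flat case the averaged risks are recovered exactly. The most extreme odds ratios (0.05 and below) need interim status entered as rows, which section 9.1 does not specify, and an assumed event timing.

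It could also be said that a statistical analysis plan, not shown here, may settle the coding. That does not remove the point, because the protocol itself fixes the three levels and names within-patient dependency as its main interest. A sensible answer would come only from discarding that level.

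**Conclusion.** Wrong as written. For the primary outcome, the patient-level variance in section 9.1 is either unidentified (one informative row, or day-9 zeros with a time term) or an artefact of the coding (day-9 zeros without a time term). The same patient outcomes, 31/155 versus 16/155, give odds ratios between 0.49 and 0.11 in these cases, against a plain 0.46. More extreme values arise only under a row layout that the protocol does not state.

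The damage is to the size and meaning of the reported odds ratio. In the simple cases the direction and the test of no effect essentially hold (likelihood-ratio statistic 5.73 or 5.26). The random hospital intercept and the use of three levels in section 9.2 are not in question. The conclusion rests on revision status being zero for everyone at day 9, and on no section defining revision as a repeated response.

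**What to change.** In section 9.1, delete the measurement level for the primary outcome. Use one record per patient (revised for PJI within one year: yes or no) in a two-level logistic model, patients within hospitals, with a random hospital intercept. Include treatment and the covariates the protocol already names, age and gender. Any further covariates are the sponsor's choice and are not needed to cure this defect. Report the two risks and their difference or ratio with a confidence interval alongside the odds ratio. Keep the three-level structure only for the repeated quality-of-life outcomes in section 9.2.

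The cost is a change of wording in section 9.1, carried into the statistical analysis plan if one exists. No new data are needed, and 155 per group (194 with dropout) stays as it is, because it already assumes one outcome per patient.

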9.2 Secondary study parameter(s)

Secondary outcomes are disease-specific and general health-related quality of life (ordinal variables). In line with the analyses of the primary outcome, a multilevel linear regression model with three levels will be used to analyse the data. The three levels are hospitals, patients and measurements, where measurements are nested within patients and patients are nested within hospitals. The effect of the intervention will be controlled with covariates such as age and gender.

